8.5 Additional Efficacy Analyses

8.5.1 At Least 50% Reduction in Palpable Splenomegaly from Baseline

The proportion of subjects who achieved at least 50% reduction in palpable splenomegaly from baseline will be analyzed using the statistical method described for binary variables in Section 8.1.

Subjects who do not have any post-baseline assessment will be treated as non-responders. Data after subjects have confirmed disease progression or start post-study treatment will be excluded from the analysis. Subjects who do not receive any study drug will be treated as non-responders. Subjects without baseline assessment will be treated as non-responders.

8.5.2 Red Blood Cell Transfusion

Post-baseline RBC transfusion evaluation period is from after the first dose of study drug to earliest day of on or before the last dose of study drug + 30 days, or the start of post-study treatment, confirmed disease progression or death, which occurs earlier.

Post-baseline transfusion independence rate will be calculated as the proportion of subjects who achieved transfusion independence during the evaluation period.

Transfusion independence is defined as a period of at least 12 weeks (≥ 84 days) with no PRBC transfusions during the evaluation period. Subjects who do not receive any study drug will be considered not achieving transfusion independence.

The duration of transfusion independence will be summarized for each treatment arm. The duration of transfusion independence is defined as the duration of the first time period in which a subject received no PRBC transfusions for at least 12 weeks (≥ 84 days). The descriptive statistics (median and range) will be provided for the duration of transfusion independence.

Incidence rate of PRBC transfusions/subject/month, defined as total number of PRBC transfusions from all subjects divided by total duration of treatment from all subjects (months), will be calculated for each treatment arm.

Time from first dose of study drug to the first time receiving 2 or more units of PRBC transfusion will be summarized for each treatment arm. The total number and amount of PRBC transfusions from each subject will be summarized for each treatment arm.

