8.0 Efficacy Analyses

8.1 General Considerations

Unless otherwise specified, all randomized subjects in the ITT population will be included in the efficacy analyses. All statistical tests will be 2-sided at an alpha level of 0.05.

The primary analysis will be performed after all ongoing subjects have completed 24 weeks of follow-up and the database has been locked. Unless otherwise specified, data after the cutoff date will be excluded from statistical analyses.

Unless otherwise specified, all subjects will be analyzed according to the baseline platelet count and DIPSS+ score collected in Electronic Data Capture (EDC) system. For subjects with missing karyotype information, the DIPSS+ score will be calculated by assuming these subjects do not have unfavorable karyotype. The DIPSS+ score will be categorized by intermediate (including both intermediate-1 and intermediate-2) and high risk.

Unless otherwise specified, binary variables (e.g., response rates) will be analyzed using Cochran-Mantel-Haenszel (CMH) test, stratified by DIPSS+ risk group (intermediate versus high risk) and platelet count ($\leq 200 \times 10^9/L$ versus $> 200 \times 10^9/L$). The 95% confidence interval for the response rate will be provided for each treatment arm using the exact binomial distribution. The strata-adjusted difference in the response rates between the treatment arms and the 95% confidence interval for the difference will also be provided.

Unless otherwise specified, continuous data from patient-reported outcome will be analyzed using linear mixed effects model with treatment arm, visit, treatment by visit interaction, DIPSS+ risk group (intermediate versus high risk), platelet count ($\leq 200 \times 10^9/L$ versus $> 200 \times 10^9/L$) and baseline score as fixed effects. An unstructured variance covariance matrix will be used. The compound symmetry variance covariance matrix will be used if the model does not converge with the unstructured matrix. Change in score from baseline will be compared between the treatment arms for the specified post-baseline visit. The least-squares mean change from baseline and the corresponding 95% confidence interval will be provided for each treatment arm. In addition, the least-squares mean of the difference between the treatment arms and the corresponding 95% confidence interval will be provided.

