Unless otherwise specified, time-to-event endpoints will be analyzed using Kaplan-Meier methodology and compared between treatment arms using the log-rank test, stratified by DIPSS+ risk group (intermediate versus high risk) and platelet count ($\leq 200 \times 10^9/L$ versus $> 200 \times 10^9/L$). The hazard ratio between treatment arms and the corresponding 95% confidence interval will be estimated using the Cox proportional hazards model, stratified by DIPSS+ risk group (intermediate versus high risk) and platelet count ($\leq 200 \times 10^9/L$ versus $> 200 \times 10^9/L$).

Unless otherwise specified, if a subject prematurely breaks the blind, data after the blind break will be included in the statistical analysis as appropriate based on the definition and analysis of the efficacy endpoints.

Unless otherwise specified, baseline refers to the last non-missing observation before the first administration of study drug or randomization if no study drug is given.

Unless otherwise specified, a confirmed disease progression is defined as any of the following:

- Two consecutive disease responses of progressive disease or relapse, in which case the date of the confirmed disease progression will be the date of the first progressive disease or relapse

- A progressive disease due to leukemic transformation
- A progressive disease or relapse that is the last disease response of a subject.

At the time this SAP is written, the evidence-based MCT for change from baseline in TSS at Week 24 is determined to be –10.

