8.4.1.9 Duration of SVR₃₅

Duration of SVR₃₅ is defined as the time from the first date of SVR₃₅ to the first assessment where SVR₃₅ is not maintained and the spleen volume is $\geq 25\%$ increase from nadir (the lowest spleen volume in the previous assessments), confirmed relapse or leukemic transformation per IWG criteria, whichever is earlier. Subjects without the

defined events will be censored at the date of the last spleen volume assessment, the last disease assessment, the last bone marrow assessment, or the last hematology lab test, whichever occurs the latest and on or prior to the start of the post-study treatment.

The distribution of duration of SVR₃₅ will be estimated for each treatment arm using Kaplan-Meier methodology. Median duration of SVR₃₅ and the corresponding 95% confidence interval will be provided for each treatment arm. There will be no statistical comparison for duration of SVR₃₅.

Only subjects who achieve SVR₃₅ will be included in the analysis.

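### Duration of transfusion independence is summarised by a plain median and range with no event or censoring rule, so the median can be too low when many periods are still open

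*SAP*

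**What the plan says.** SAP 8.5.2 sets the threshold: "Transfusion independence is defined as a period of at least 12 weeks (≥ 84 days) with no PRBC transfusions during the evaluation period". The duration is the length of the first such period, and "The descriptive statistics (median and range) will be provided for the duration of transfusion independence". The evaluation period runs from after the first dose to the "earliest day of on or before the last dose of study drug + 30 days, or the start of post-study treatment, confirmed disease progression or death". Under SAP 8.1, "data after the cutoff date will be excluded from statistical analyses", so the cutoff is a further stopping point. Section 8.5.2 does not say what ends a period, or what to do with one that has not ended. It also does not limit the duration summary to subjects who were transfusion dependent at baseline.

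The SAP's other response durations are handled differently. The distribution of duration of SVR35 (SAP 8.4.1.9) "will be estimated for each treatment arm using Kaplan-Meier methodology", with stated events, a stated censoring date and a 95% CI for the median, although no comparison of arms is planned. Duration of TSS50 and duration of TSS response (SAP 8.4.1.1) are treated in the same way.

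**The concern.** Transfusion independence has an onset, a possible later loss and incomplete follow-up, as the SAP's other response durations have. A plain median mixes finished periods with periods cut short because observation stopped. It then reflects follow-up as well as durability.

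Open periods are likely to be common at the first report. By SAP 8.1, "The primary analysis will be performed after all ongoing subjects have completed 24 weeks of follow-up". A subject with only that minimum follow-up who is transfusion independent from the first dose can be recorded at no more than about 24 weeks, that is 24 × 7 = 168 days against a threshold of 84. For a subject who is never transfused, the recorded duration is simply the length of the evaluation period.

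Randomisation is 1:1, so calendar follow-up should be similar by arm. Last dose, progression and start of other treatment occur after randomisation and may differ. Two arms with equal durability could then show different medians side by side. What is at stake is a descriptive durability figure, not a test.

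**Working it through.** **Plan's own figure.** There is none to reproduce. Neither document gives a duration, a discontinuation rate or an expected share of open periods. The distributions below are assumptions.

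**General result.** Let T be the true length of the period and C the time from its start to the end of observation, with T and C independent. The recorded length is min(T, C). The plain median m solves S_T(m) × S_C(m) = 0.5, while the true median M solves S_T(M) = 0.5. Since S_C ≤ 1, m cannot exceed M. The two are equal when S_C(M) = 1, that is, when nobody's observation stops before M.

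**Illustration 1 (months).** T = 3 + exponential with M = 12, so the rate is ln 2 / (12 − 3) = 0.0770. C is uniform over its mean ± 6 months.

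| Mean C | Plain median m | S_T(m) | S_C(m) | Product | Periods open |
|---|---|---|---|---|---|
| 9 | 6.9 | exp(−0.0770 × 3.9) = 0.741 | (15 − 6.9)/12 = 0.675 | 0.50 | 65% |
| 12 | 8.7 | exp(−0.0770 × 5.7) = 0.645 | (18 − 8.7)/12 = 0.775 | 0.50 | 52% |
| 15 | 10.4 | exp(−0.0770 × 7.4) = 0.566 | (21 − 10.4)/12 = 0.883 | 0.50 | 41% |

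The share open is the mean of S_T(C). For the first row it is (1 − exp(−12 × 0.0770))/(12 × 0.0770) = 0.65. The next two rows multiply this by exp(−3 × 0.0770) and exp(−6 × 0.0770), giving 0.52 and 0.41. Kaplan-Meier, with open periods censored, gave 12.0 in simulation each time.

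**Illustration 2 (weeks, varying the true median).** T = 12 + exponential. Follow-up is uniform over 24 to 72 weeks, the median time to discontinuation is 52 weeks, and observation ends 30 days after that. Subjects observed for under 12 weeks are dropped. There are 200,000 simulated subjects per scenario.

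| True median | Plain median | Kaplan-Meier median | Periods open |
|---|---|---|---|
| 24 | 21.7 | 24.0 | 29% |
| 36 | 27.0 | 36.0 | 49% |
| 52 | 30.1 | 52.1 | 64% |
| 104 | 34.1 | not reached | 82% |

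**Dependence on follow-up.** With a true median of 52 weeks and no discontinuation, the plain median is 35.8 for follow-up of 24–72 weeks, 40.8 for 24–120 and 52.2 for 96–192.

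**Dependence on arm.** With a true median of 52 weeks in both arms and follow-up of 24–120 weeks, the plain median is 31.9 if the median time to discontinuation is 52 weeks and 35.6 if it is 104. The gap of 35.6 − 31.9 = 3.7 weeks is spurious. Kaplan-Meier gave 51.8 and 51.9.

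**No-bias case.** With a true median of 24 weeks, follow-up of 48–96 weeks and no discontinuation, both methods give 24.1.

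**Limit of these runs.** All assume that the end of observation is independent of the transfusion risk. In an illustrative run with the two risks correlated, Kaplan-Meier gave 15.5 months against a true 13.7, and the plain median gave 7.6. Kaplan-Meier was closer but not unbiased.

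**The case against.** The strongest reply is that the SAP does not actually prescribe a wrong calculation. Section 8.5.2 is silent on open periods, and SAP 8.1 provides a default: "Unless otherwise specified, time-to-event endpoints will be analyzed using Kaplan-Meier methodology". A median can be read from a Kaplan-Meier curve. This does not carry far. The default yields where a section specifies something else, and 8.5.2 specifies descriptive statistics. The general censoring rule in SAP 8.2 relies on a censoring date defined for the endpoint, and 8.5.2 defines none. The plain median is the natural reading, but it is a reading.

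A reader might go further and infer that the reported median is bound to be too low, or that a between-arm conclusion will be wrong. The documents support neither. The bias depends on how many periods are open and how long they already are, and no arm comparison of these durations is planned.

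Three other points stand. First, RBC transfusion is an exploratory endpoint (Protocol 3.3; SAP 3.3) and is absent from the testing sequence in SAP 12.0, Table 1. Second, the same section reports the transfusion independence rate, a transfusion rate per subject-month, and the number and amount of transfusions; anemia response, which includes a 12-week transfusion-free criterion, is formally tested. Third, simply censoring at the end of the evaluation period would censor progression and death without saying so, and that censoring may be informative.

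**Conclusion.** The point holds as a conditional one. As written, SAP 8.5.2 lets truncated periods into a plain median. When open periods are common and shorter than the true median, the result is too low and varies with time on treatment. When every open period is already longer than the median, nothing changes.

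The size cannot be taken from the documents. In the illustrations the plain median ranges from no error, through 6.9 to 10.4 months against an assumed 12, to 34.1 weeks against an assumed 104. These figures rest on assumed duration distributions and independent censoring. Type I error, the primary endpoint and the ranked secondary endpoints are untouched. This is a low-priority correction, worth making because the SAP already uses the better method for its other response durations.

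**What to change.** In SAP 8.5.2, estimate the duration by Kaplan-Meier among subjects who achieve transfusion independence. Take the next PRBC transfusion as the event, and censor periods still open at the end of the evaluation period or at data cutoff. State explicitly whether confirmed progression and death count as events or are censored, and run the other choice as a sensitivity analysis. SAP 8.4.1.9 counts confirmed relapse and leukemic transformation as events for duration of SVR35, so the two sections should either agree or explain the difference. Report the median with 95% CI and the number of periods ongoing, by arm.

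The cost is a few sentences of SAP text, one decision on progression and death, and a procedure already used elsewhere in the plan; no new data are needed. There are two downsides. The median may be not reached, and censoring at progression or discontinuation may be informative, in which case Kaplan-Meier could overstate durability.

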8.5.3 EORTC QLQ-C30

Scores for the subscales/items from the EORTC QLQC30 will be calculated according to the scoring manuals. Change in scores from baseline will be analyzed using the linear mixed effects model described in Section 8.1.

8.5.4 Progression-Free Survival (PFS)

Progression-free survival is defined as the time from randomization to the date of confirmed relapse or progressive disease, or death from any cause, whichever occurs earlier, on or prior to the start of post-study treatment. Subjects without any defined PFS event will be censored at the date of last adequate disease assessment on or prior to the start of post-study treatment. Subjects who are alive and without any adequate disease assessment will be censored at the date of randomization.

Progression-free survival will be analyzed using the statistical method described for time-to-event variables in Section 8.1.

8.5.5 Change in Frequency of Allelic Mutations from Baseline

Absolute change and percent change from baseline in variant allele frequency any time during the post baseline period will be derived by specific driver gene, which is mutated- JAK2, -CALR, and -MPL, if baseline allele frequency and post-baseline allele frequency are available based on the Next generation sequencing (NGS) method in the peripheral blood.

Descriptive analysis will be performed to analyze the change from baseline in variant in driver gene allele frequency at different time points. Waterfall and line plots will be used for visualization. The proportion of subjects who achieved $\geq 20\%$ and $\geq 50\%$ reduction in driver gene allele frequency at Week 24 and at any time will be summarized for each treatment arm.

8.5.6 EQ-5D-5L

Scores for EQ-5D-5L⁷ and its visual analog scale will be calculated according to the scoring manuals. Change in scores from baseline will be analyzed using the linear mixed effects model described in Section 8.1.

8.5.7 PROMIS Fatigue 7a

Scores for PROMIS Cancer Fatigue 7a symptom items and impact items will be calculated according to the scoring manuals. All questions of a subdomain must be answered to calculate a score for that subdomain. The score for a subdomain will be calculated as the average of the item scores in that subdomain. Change in scores from baseline will be analyzed using the linear mixed effects model described in Section 8.1. Raw scores will be used in the analysis.

8.5.8 Overall Response of Clinical Improvement

Rate of overall response of clinical improvement is defined as the proportion of subjects who achieve best response of clinical improvement (CI) per IWG criteria. Subjects who do not have any disease assessment or who have started post-study treatment prior to achieving best response of CI will be treated as non-responders. Responses achieved after confirmed relapse or progressive disease will not be included in the analysis.

Rate of overall response of clinical improvement will be analyzed using the statistical method described for binary variables in Section 8.1.

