3.3 Exploratory Endpoints

Exploratory endpoints:

- At least 50% reduction in palpable splenomegaly from baseline per IWG criteria
- Red blood cell (RBC) transfusion during study drug treatment
- Change in quality of life from baseline as measured by the global health status/quality of life domain of the EORTC QLQ-C30
- Change in the summary score for the EORTC QLQ-C30 from baseline
- Progression-free survival (PFS) per IWG criteria
- Change in frequency of allelic mutations from baseline
- Change in EuroQol 5 Dimensions 5 Levels Health State Instrument (EQ-5D-5L) from baseline
- Change in fatigue-related symptoms from baseline as assessed by the PROMIS Fatigue 7a symptom items
- Change in impacts associated with fatigue from baseline as assessed by the PROMIS Fatigue 7a impact items.
- Translational biomarkers and correlation with clinical outcomes.
- Overall response of clinical improvement per IWG criteria
- At least 50% reduction in TSS at Week 24 from baseline (TSS_{50W24})
- Time to first TSS₅₀
- Duration of TSS₅₀
- TSS response rate at any time based on meaningful change threshold (MCT)
- Time to first TSS response
- Duration of TSS response

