MRI	Magnetic resonance imaging
mRNA	messenger ribonucleic acid
NCI	National Cancer Institute
NRS	Numeric rating scale
NSAID	nonsteroidal anti-inflammatory drug
OS	Overall survival
PBMC	Peripheral blood mononuclear cell
PCP	Pneumocystis carinii pneumonia
PET	Post essential thrombocythemia
PFS	Progression-free survival
PGIC	Patient Global Impression of Change
PGIS	Patient Global Impression of Severity
P-gp	P-glycoprotein
PK	Pharmacokinetic
Plt	Platelet
PMF	Primary myelofibrosis
PPD	Purified protein derivative
PPV	Post polycythemia vera
PR	Partial remission
PRO	Patient-reported outcome
PROMIS	Patient-Reported Outcomes Measurement Information System
PT	Prothrombin time
Q12	Every 12 (weeks)
Q24	Every 24 (weeks)
QLQ	Quality of life questionnaire

QoL	Quality of life
QTc	QT interval corrected for heart rate
QTcF	QT interval corrected for heart rate using Fridericia's formula
RBC	Red blood cell
RNA	Ribonucleic acid
RPTD	Recommended Phase 2 dose
RSI	Reference Safety Information
SAE	Serious adverse event
SAP	Statistical analysis plan
SAR	Serious adverse reaction
SARS-CoV-2	Severe acute respiratory syndrome coronavirus 2
SDAC	Statistical data analysis center
SF	Short form
SMF	Secondary myelofibrosis
SmPC	Summary of product characteristics
SOC	System organ class
SSRI	Selective serotonin re-uptake inhibitors
SUSAR	Suspected unexpected serious adverse reaction
SVR ₃₅	At least 35% spleen volume reduction from baseline
SVR _{35W24}	At least 35% reduction in spleen volume at Week 24 from baseline
TA MD/SD	Therapeutic Area Medical Director/Scientific Director
TB	Tuberculosis
TCV	Treatment completion visit
TSS	Total symptom score
TSS _{50W24}	At least 50% reduction in total symptom score at Week 24 from baseline
ULN	Upper limit of normal
USA	United States of America
USPI	United States prescribing information
v	Version
VAS	Visual analogue scale
V/F	Apparent volume of distribution
WBC	White blood cell
WHO	World Health Organization

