4.0 Analysis Populations

The following population sets will be used for the analyses.

The Intent-to-Treat (ITT) Population includes all randomized subjects. Unless otherwise specified, the ITT Population will be used for all efficacy analyses. Subjects will be included in the analysis according to the treatment arms that they are randomized to.

The TSS Sensitivity Analysis Population includes all randomized subjects who meet the following criteria:

- subjects with baseline TSS score ≥ 12 ; or
- subjects with at least 2 symptoms with a baseline symptom score ≥ 3 .

The Safety Analysis Set consists of all subjects who received at least 1 dose of any component of the study drug. Subjects will be included in the analysis according to the study drug that they actually received.

The pharmacokinetic (PK) analysis population consists of all subjects who received at least 1 dose of navitoclax. The PK analysis population will be used for all PK analyses.

The study drug is defined as any component of navitoclax + ruxolitinib for subjects in Arm A and any component of placebo + ruxolitinib for subjects in Arm B.

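### Read literally, the clinical-improvement rate in SAP 8.5.8 leaves out subjects whose best IWG response is a remission; the numerator should say CI or better

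*SAP*

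**What the plan says.** SAP 8.5.8 (Overall Response of Clinical Improvement) takes the rate to be the "proportion of subjects who achieve best response of clinical improvement (CI) per IWG criteria". Its non-responder rule covers subjects with no disease assessment and those "who have started post-study treatment prior to achieving best response of CI will be treated as non-responders". A further sentence limits the period that counts: "Responses achieved after confirmed relapse or progressive disease will not be included in the analysis". The rate is then compared between arms by the general method for binary variables in SAP 8.1: a stratified Cochran-Mantel-Haenszel (CMH) test with a strata-adjusted difference and its 95% confidence interval.

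The section names no other analysis set, so the default in SAP 4.0 applies: "Unless otherwise specified, the ITT Population will be used for all efficacy analyses". Protocol 3.3 lists the endpoint among the exploratory ones, as "Overall response of clinical improvement per IWG criteria", with no mention of best response.

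Neither document reproduces the IWG response categories or their order. Remission appears in Protocol Appendix A, where the abbreviation PR is expanded as "Partial remission". SAP 8.1 lists relapse beside progressive disease as a recorded outcome, in its definition of confirmed progression: "Two consecutive disease responses of progressive disease or relapse".

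**The concern.** A best response is one category per subject, chosen over all assessments. If the numerator is a single middle category, a subject who does better than that category is not counted. The rate then stops rising with the quality of response: moving a subject from CI to a remission lowers it.

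The endpoint lists in SAP 3.1 to 3.3 contain no remission rate, so a remission missed in 8.5.8 is not picked up by another planned overall-response rate. Two competent programmers could also code the section differently, one as best response equal to CI and the other as CI or better. That choice should not be left until treatment assignments are known.

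**Working it through.** The plan states no expected rate, power or sample size for this endpoint, so there is no figure to reproduce. The check is a reading of the text, followed by arithmetic for scale.

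**Reading the text**

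1. Numerator: SAP 8.5.8 names one category, CI, in the definition and again in the non-responder sentence. Neither place adds an *or better*.
2. Contrast: the SAP's other response endpoints are worded as minimums. This holds for spleen volume (8.4.1.2), symptom score (8.4.1.1), marrow fibrosis grade (8.4.1.6) and palpable spleen (8.5.1). Section 8.5.8 is the exception.
3. Denominator: all randomized subjects, by the default in SAP 4.0.
4. Result: a subject whose best category is a remission is in the denominator and not in the numerator, which is arithmetically a non-response.

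**Size**

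Input from the documents: about 230 subjects randomized 1:1 (Protocol 7.7, SAP 2.4), so 230 / 2 = 115 per arm.

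Effect of one subject on an arm's rate: 1 / 115 = 0.87, or about 0.9 percentage points.

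Let A and B be the true rates of CI or better in Arms A and B, and rA and rB the shares whose best response is a remission. The literal rule gives

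(A − rA) − (B − rB) = (A − B) − (rA − rB).

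The difference therefore shifts by rA − rB and by nothing else. For illustration, **assume** A = 55% and B = 40%; neither rate is in the documents. The true difference is then 15 points.

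| rA | rB | Literal rate, Arm A | Literal rate, Arm B | Literal difference | Subjects leaving the numerator (A; B) |
|---|---|---|---|---|---|
| 0% | 0% | 55% | 40% | 15 points | 0; 0 |
| 2% | 0% | 53% | 40% | 13 points | 2.3; 0 |
| 5% | 0% | 50% | 40% | 10 points | 5.8; 0 |
| 10% | 0% | 45% | 40% | 5 points | 11.5; 0 |
| 2% | 2% | 53% | 38% | 15 points | 2.3; 2.3 |
| 0% | 2% | 55% | 38% | 17 points | 0; 2.3 |

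Subject counts are the share times 115, for example 0.05 × 115 = 5.75. Equal remission shares leave the difference alone. Remissions in the control arm only would inflate it.

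**The case against.** The best case for the plan is that 8.5.8 never restricts the count to CI alone and no sentence mentions remission. The phrase about starting other treatment before CI is reached can be read as treating CI as a milestone, and the endpoint's name is compatible with at least CI. This stands in part: the strict reading is the literal one, but it is not proven to be the intended one. It does not remove the problem, because nothing elsewhere in either document adds remissions to the numerator.

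A second objection is that the ranking cannot be checked. Both documents cite the IWG consensus report without reproducing its categories, and an entry in an abbreviation list does not show that partial remission is recorded in this assessment. Relapse as a recorded outcome suggests categories above progression but gives no order. This stands, and the ranking is carried below as an assumption.

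Three stronger conclusions are tempting, and the documents do not support them:

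- *The rule biases the comparison against navitoclax.* That needs more remissions in Arm A than in Arm B, and neither document gives a remission rate for either arm.
- *The rule would cut the effect sharply, for instance by half.* Any such figure depends on assumed rates. The Study M16-109 results in Protocol 2.1 cover spleen, symptom and fibrosis responses and report no remissions.
- *The rule penalises the disease modification that the trial is looking for.* The clinical hypothesis in Protocol 2.1 names spleen response and its durability, symptoms, fibrosis and allelic burden. Each has its own analysis in the SAP, and remission is not named.

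**Conclusion.** The point holds as a flaw in the literal definition. As written, a subject whose best IWG response is a remission is left out of the numerator and kept in the denominator, at a cost of about 0.9 points per subject to that arm's rate. The between-arm difference moves only by the gap in remission shares. That gap is not given and may be zero, in which case nothing changes.

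This rests on three assumptions: that best response is a single category per subject, that the IWG criteria place at least one remission category above CI, and that the section is programmed as worded. The table rates are illustrative only.

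The consequence is small. The endpoint is exploratory in Protocol 3.3, sits among the other efficacy endpoints in SAP 3.3, and is absent from the testing sequence in SAP Table 1. No ranked conclusion, the primary one included, depends on it, and type I error control is untouched. It is a desirable correction, not a necessary one.

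**What to change.** In SAP 8.5.8, define the numerator as subjects with a best response of *CI or better (CI or any IWG remission category)*. Use the same phrase in the non-responder sentence; otherwise a subject who reached remission and later began other treatment could be read as never having reached CI. Keep the existing exclusion of responses after confirmed relapse or progression.

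If a CI-only rate is really intended, say so and report remissions by arm on a separate line.

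The cost is a few words in one section and one line of code. It needs no new data and changes no other analysis. It should be settled before unblinding.
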